5.1.3. INCB050465 and R-ICE Combination Therapy

Subjects enrolled into Part 6 of the study will receive INCB050465 continuously in 21-day cycles. INCB050465 should be administered in the clinic on Days 1 and 15 of Cycle 1. The R-ICE chemotherapy regimen will be administered as described below for 3 cycles, which will be 21 days each. INCB050465 may be continued until a criterion is met for treatment discontinuation.

- Rituximab 375 mg/m² given on Day 1 and Day 2 of Cycle 1 and on Day 1 of Cycles 2 and 3.
- Ifosfamide 5000 mg/m² continuous IV infusion over 24 hours on Day 3 of each cycle.
 - Mesna will be infused with ifosfamide.

- Carboplatin area under the curve = 5 (maximum dose 800 mg) IV infusion on Day 3 of each cycle.
- Etoposide 100 mg/m² IV on Days 3 to 5 of each cycle.

Note: As an alternative to the Protocol-specified dose and schedule, R-ICE may be administered per institutional practice with medical monitor approval.

5.2. Treatment Compliance

Subjects should be counseled by the investigator to maintain strict adherence to the study regimen as prescribed and to keep a record of any missed doses. Subject diaries will be provided for the purposes of keeping accurate documentation of study drug administration and treatment compliance. The subject will be instructed to bring all unopened, empty, and opened/partially used bottles of study drug to each study visit, at which time compliance will be assessed.

5.3. Randomization and Blinding

Not applicable.

5.4. Duration of Treatment and Subject Participation

Subjects in Parts 1, 2, and 3 will be treated in continuous 21-day cycles indefinitely; this may include temporary interruptions described in Section 5.6. Subjects in Part 6 will be treated in 21-day cycles. INCB050465 may continue indefinitely, but R-ICE will only be given for 3 cycles.

Subjects who have evidence of objective clinical benefit, regardless of dose level, may continue to be treated at that dose level. Dose and schedule changes may be implemented for ongoing subjects based on emerging tolerability data. If study drug is permanently discontinued (for reasons, see Section 5.6.2.1) the subject will be withdrawn from the study. Treatment duration will vary among subjects, but is expected to average approximately 6 months.

5.5. Rationale for Dose Modification

Selections and modifications to the dosage of study drug are planned for dose-escalation cohorts. Also, dose interruptions and modifications may occur for individual study subjects. The identification of DLTs will define the doses used in planned cohorts. Further, the occurrence of DLTs and other toxicities will guide decisions for treatment interruptions and discontinuation for individual subjects.

Subjects enrolled in lower doses in the dose-escalation portion of the study will have the option of escalating to a dose found to be tolerated in a subsequent cohort provided the criteria specified in Section 5.6.1 are met.

5.5.1. Dose-Limiting Toxicity

A DLT is any AE noted in Table 3. DLTs include all AEs of the specified grades, regardless of investigator attribution of relatedness. AEs occurring during Cycle 1 of the dose-escalation portion of the study will be considered to be DLTs if they are not clearly related to the underlying disease, its progression, a comorbidity, concomitant medication, or transient

(≤ 72 hours) abnormal laboratory values without associated clinically significant signs or symptoms based on investigator determination. Events not meeting these precise criteria may be considered DLTs as determined during review by the Incyte medical monitor and principal investigators.

Individual subject dose reductions may be made based on events observed at any time during treatment with INCB050465; however, for the purposes of dose cohort escalation/de-escalation, expanding a dose cohort, and determining the MTD or recommended dose of INCB050465, decisions will be made based on events deemed to be DLTs that are observed from the first day of INCB050465 administration through and including the final day of Cycle 1 (Day 21 or Day 28 depending on the part of the study that the subject has been enrolled to); in addition, all safety data available to date will be considered.

Each dose cohort in this study will be reviewed before dose escalation by the Incyte medical monitor and principal investigators. Telephone conferences will be scheduled by the sponsor with all investigators in order to review cohort-specific data and overall safety data from prior cohorts (if applicable), and to agree on dose escalation and the recommended dose for Phase 2 per DLT rules defined in this section.

Dose-limiting toxicities will be assessed by the investigator using the current CTCAE version 4.03 criteria. All toxicities will be graded based on the highest grade that is actually reached, rather than the level that might have been reached if left untreated. A DLT will be defined as any AE that is new in onset or worsening in severity and meets any of the criteria listed in [Table 3](#).

Table 3: Definition of Dose-Limiting Toxicity

Nonhematologic:

 • ≥ Grade 3 nonhematologic toxicity, excluding nausea, vomiting, diarrhea. • ≥ Grade 3 nausea, vomiting, or diarrhea uncontrolled by maximal antiemetic/antidiarrheal therapy lasting > 48 hours. • Any toxicity considered a DLT in the opinion of the investigator and medical monitor.
Hematologic:

 • Grade 4 neutropenia lasting ≥ 7 days. NOTE: INCB039110 is suspected to cause transient decreases in white blood cells due to margination, therefore, DLT rules require neutropenia to persist after holding INCB039110 for 2 to 3 days. Where the clinical status of the subject allows, investigators are encouraged to wait 24 hours before starting growth factors, to determine if white blood cell margination is contributing to the degree of neutropenia. • Febrile neutropenia (ANC < 1.0 × 10⁹/L with a single temperature of > 38.3°C (101°F) or a sustained temperature of ≥ 38°C (100.4°F) for more than 1 hour). • Grade 3 thrombocytopenia associated with clinically significant bleeding (clinically significant as determined by the investigator or resulting in the need for a transfusion of red blood cells). • Grade 4 thrombocytopenia lasting > 7 days. • Grade 4 anemia.
General:

 • Any specific AE that results in a dose delay or reduction in > one-third of subjects.

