1.2.4. Clinical Summary of INCB050465

As of 02 SEP 2016, data were available for 46 subjects who received INCB050465 administered orally at QD doses of 5 mg (n = 1), 10 mg (n = 3), 15 mg (n = 3), 20 mg (n = 15), 30 mg (n = 20), and 45 mg (n = 4). The median duration of treatment was 104 days. Adverse events observed in $\geq 20\%$ of subjects were nausea, diarrhea, vomiting, neutropenia, fatigue, hypokalemia, and fever. No \geq Grade 3 treatment-related AEs were reported in $\geq 10\%$ of subjects. Serious AEs (SAEs) that occurred in ≥ 2 subjects included colitis (n = 3), diarrhea (n = 3), and pyrexia, pneumonia, dehydration, exfoliative dermatitis, and hypotension (n = 2 each). Eleven of the 46 subjects (24%) discontinued study treatment due to the following AEs: colitis, diarrhea, pneumonitis, rash, exfoliative dermatitis, psoriasis, neutropenia, pneumonia, and hypercalcemia. All but 1 of these events occurred after the 9-week disease assessment. No liver function test abnormalities > Grade 1 were reported while subjects were receiving study treatment. No dose-limiting toxicities were identified, and the maximum tolerated dose was not reached.

As of 02 SEP 2016, 20 objective responses as reported by investigators were observed at doses ≥ 10 mg QD in 41 evaluable subjects. Objective responses were observed in 5 subjects with DLBCL (n = 14), 6 subjects with follicular lymphoma (n = 6), 4 subjects with marginal zone lymphoma (n = 4); 3 subjects with mantle cell lymphoma (n = 4), 1 subject with Hodgkin lymphoma (n = 8), and 1 subject with CLL (n = 5). The objective response rate in evaluable subjects with NHL (n = 28) was 64%. Among the 18 objective responses observed in subjects with NHL, 17 (94%) were observed by the time of the first disease assessment.

Pharmacokinetics analysis showed the T_{max} is 0.5 to 1 hour, the terminal half-life is approximately 8 to 12 hours, and exposure appeared to be dose-proportional between 5 mg QD and 45 mg QD at steady state. The pharmacodynamic analyses demonstrated robust and sustained pathway inhibition at all dose levels tested. Refer to the [INCB050465 IB](#) for further details.

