and INCB039110 may be restarted (see [Table 4](#)). Dose reductions of 1 or both (as applicable for subjects on combination therapy) study treatments may be necessary as described in [Table 4](#). For subjects who start on the 300 mg QD dose of INCB039110, the first dose reduction would be to 200 mg QD. If subjects start at a 200 mg QD dose of INCB039110, the combination of INCB050465 with INCB039110 at a lower dose (eg, 100 mg QD) will be subject to discussion with the sponsor. Alternatively, INCB039110 may be discontinued if dose reduction is indicated, and subjects may continue on INCB050465 monotherapy if they continue to receive benefit.

Because subjects may enter the study with extensive pretreatment and/or severe bone marrow infiltration by the primary disease, these dose-reduction rules are provided as guidelines. Individual decisions regarding dose reduction should be made using clinical judgment and in consultation with the sponsor's medical monitor, taking into account relatedness of the AE to the study drug and the subject's underlying condition. Subjects receiving dose reductions (but not meeting DLT criteria) during the first cycle will not be considered evaluable for the purposes of determining the MTD.

Table 4: Guidelines for Interruption and Restart of Study Drug

TOXICITY/NCI CTCAE GRADE	ACTION TAKEN
Chemistries:	

 Total bilirubin > 3.0 × ULN AST and/or ALT > 3.0 × ULN ALP ≥ 2.5 × ULN 
Note: For ALP increases in subjects with bone metastasis-related ALP elevation at baseline, contact sponsor to discuss clinical management and possible dose reductions.
	
Step 1: Interrupt study drug(s) up to 2 weeks (14 days) until the toxicity has resolved to ≤ Grade 1 except ALT/AST elevations, which may require 4 weeks (28 days) to resolve.
 
Step 2: Restart study drug(s) at next lower dose (or INCB050465 at 25% reduction if in expansion cohorts, rounded down to the nearest pill strength); monitor as clinically indicated.^a
 
Dose reductions may be made solely to the suspected agent if the causality can be reasonably assigned to that agent based on existing data (refer to the INCB050465 IB and INCB039110 IB) with approval of the medical monitor.

Hematologic:	

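### The DLT table counts Grade 3 thrombocytopenia with significant bleeding, but leaves short Grade 4 thrombocytopenia with the same bleed (below Grade 3) to discretion

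*Protocol*

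**What the plan says.** Table 3 in Protocol Section 5.5.1 has two platelet criteria:

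- "Grade 3 thrombocytopenia associated with clinically significant bleeding". Significance rests on the investigator's judgement or on a need for red cell transfusion. No minimum duration is set.
- "Grade 4 thrombocytopenia lasting > 7 days". This line does not mention bleeding.

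The text above the table sets the grading rule: "All toxicities will be graded based on the highest grade that is actually reached".

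Several other provisions bear on the same event:

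- A nonhematologic toxicity of Grade 3 or higher is a DLT, apart from nausea, vomiting and diarrhea, which have their own line.
- Grade 4 anemia is a DLT.
- The General line covers a specific adverse event that delays or reduces dosing in more than one-third of subjects.
- Table 3 also lists "Any toxicity considered a DLT in the opinion of the investigator and medical monitor".
- Section 5.5.1 adds: "Events not meeting these precise criteria may be considered DLTs as determined during review".
- It also provides for review: "Each dose cohort in this study will be reviewed before dose escalation". Dose decisions take account of all available safety data as well as DLTs.

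Section 5.6.2 says: "Subjects receiving dose reductions (but not meeting DLT criteria) during the first cycle will not be considered evaluable" for the maximum tolerated dose (MTD). The SAP (Section 8.2.2) only lists DLTs and gives no definition of its own.

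**The concern.** The two platelet lines do not nest. Once platelets reach Grade 4, the grading rule takes the event out of the Grade 3 bleeding line, and the Grade 4 line then asks for more than 7 days whether or not the subject bled. The worse platelet event gets the softer rule.

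DLT counts drive the 3 + 3 decisions (Sections 4.2.1, 4.2.2 and 4.2.4) and the expansion stopping rules (Sections 4.2.3 and 4.2.4). If the discretionary clauses are not used, one of two things happens. A subject whose dose is reduced in Cycle 1 becomes non-evaluable for the MTD. Otherwise the subject counts as DLT-free.

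The event is most plausible in Part 6 with R-ICE, since Section 1.5.2.3.2 warns that etoposide can cause severe myelosuppression leading to bleeding. For monotherapy, Section 1.2.4 reports on 46 subjects: "No dose-limiting toxicities were identified, and the maximum tolerated dose was not reached".

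**Working it through.** **Text check.** Take one subject with Grade 4 platelets for 7 days or less and a clinically significant bleed below Grade 3, and apply each route in Section 5.5.1.

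| Route | Met? |
|---|---|
| Grade 3 platelets with bleeding | No: the event is graded 4 |
| Grade 4 platelets for more than 7 days | No: too short |
| Nonhematologic, Grade 3 or higher | No: the bleed is below Grade 3 |
| Grade 4 anemia | No, unless it also occurs |
| General line | Not by one event in a cohort of 3: 1/3 is not more than one-third |
| Investigator and medical monitor opinion | Possible, discretionary |
| Pre-escalation review | Possible, discretionary |

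With Grade 3 platelets and the same bleed, the first row is met and the event is a DLT.

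Two readings that might close the gap fail. Grade 3 cannot be taken to mean Grade 3 or higher, because the same table uses ≥ Grade 3 in two nonhematologic lines. The exclusion for laboratory abnormalities of 72 hours or less applies only without clinically significant signs or symptoms, and a significant bleed is such a sign.

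**The protocol's own figure.** For a per-subject DLT rate r, a 3 + 3 cohort escalates with 0 DLTs in 3, or with 1 in 3 followed by 0 in the next 3:

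P(escalate) = (1 − r)³ + 3r(1 − r)⁵

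At r = 10, 20, 30, 40, 50 and 60% this gives 90.6, 70.9, 49.4, 30.9, 17.2 and 8.2%, which is Table 13 (Section 9.2) exactly. That table is not in dispute.

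**Inputs for the size.**

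- q, the per-subject rate of the uncounted event: not in the documents. Assumed 0.1% to 1%.
- p, the background DLT rate: assumed 5% or 20%. For 0 DLTs in 46 monotherapy subjects, the one-sided 95% upper limit is 1 − 0.05^(1/46) = 6.3%, if all 46 were DLT-evaluable, so 5% is compatible. The 20% is an assumption for the combinations, which those data do not cover.

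**Escalation.** As written, r = p. If the event is counted, r = p + q. For example, at p = 20%, 0.8³ + 3(0.2)(0.8)⁵ = 0.5120 + 0.1966 = 70.86%. With q = 1%, 0.79³ + 3(0.21)(0.79)⁵ = 0.4930 + 0.1939 = 68.69%.

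| p | As written | q = 0.1% | q = 0.5% | q = 1% |
|---|---|---|---|---|
| 5% | 97.34% | 97.24% | 96.83% | 96.27% |
| 20% | 70.86% | 70.64% | 69.78% | 68.69% |

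The drop is 0.1 to 1.1 points at p = 5% and 0.2 to 2.2 points at p = 20%.

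The as-written column treats the affected subject as DLT-free. If the subject is replaced instead, the rate among evaluable subjects is p/(1 − q). At q = 1% escalation is then 97.29% (p = 5%) or 70.42% (p = 20%). The drop when the event is counted becomes 97.29 − 96.27 = 1.0 point, or 70.42 − 68.69 = 1.7 points.

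**Expansion stop.** For 5 or more DLTs in 15 subjects, exact binomial:

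| p | As written | q = 0.1% | q = 1% |
|---|---|---|---|
| 5% | 0.061% | 0.067% | 0.140% |
| 20% | 16.42% | 16.68% | 19.10% |

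All these differences ignore the opinion line, the review and the General line, so each is an upper limit for its q.

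**The case against.** The strongest reply is that this is a one-symbol slip with a working safety net. The opinion route is itself a Table 3 criterion, every cohort is reviewed before escalation, and all available safety data are considered, so a Grade 4 platelet event with a significant bleed would be seen whatever its label. The Grade 3 line also rests partly on the investigator's judgement. Table 4 directs interruption and then a lower dose for its lowest platelet bands, so the subject would more naturally be non-evaluable than DLT-free. Section 4.2.1 also allows replacement in Part 1 when a subject has fewer than 17 days at the assigned dose. How many transfused bleeds fall below Grade 3 depends on CTCAE v4.03, which is not reproduced. Part 1 reached 45 mg with no DLT, and Section 1.7.1 bases the 20 mg regimen on target coverage, responses and discontinuations.

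Most of this stands as a limit on the consequence. The event would probably be counted, replacement is a fair comparator, the rates are assumptions, and nothing suggests that the Part 1 dose choice turned on this line. That evidence does not reach Parts 2 and 6.

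None of it corrects the rule. The safeguards either leave the event to judgement or remove the subject from the MTD assessment without scoring a DLT. The review is also meant to agree escalation under the DLT rules of Section 5.5.1, so the faulty wording is what reviewers apply.

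**Conclusion.** The concern holds and is minor. As written, Table 3 ranks the two platelet events the wrong way round for one narrow case: Grade 4 for 7 days or less, with a significant bleed below Grade 3 and no Grade 4 anemia. Confidence in the reading of the text is high.

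The practical size is small and rests on assumed rates. At an event rate of 1%, the effect is about 1 to 2 points on the chance of escalation and 0.1 to 3 points on the expansion stop. At 0.1% it is at most 0.2 and 0.3 points. The real effect is likely to be smaller, because the discretionary routes would usually work.

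**What to change.** Put ≥ before Grade 3 in the Table 3 bleeding line, and keep the separate line for Grade 4 thrombocytopenia beyond 7 days.

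Under Amendment 10 only the schedules in Tables 9 and 10 apply, and they contain no Cycle 1 visit, so the practical use is retrospective. Before the DLTs and the MTD or recommended dose are reported, re-read existing Cycle 1 Grade 4 platelet events with bleeding in all parts. Include subjects who were dose-reduced or replaced. Mark any DLT added this way as identified by the re-read, because the corrected wording was not in force when doses were chosen.

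No new output is needed: Protocol Section 9.4.3.1 already lists Cycle 1 DLTs without restricting the study part. The cost is one symbol and a short review of platelet and bleeding data. The only downside is possibly one more counted DLT.

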5.5.2. Follow-Up of Dose-Limiting Toxicities

Any DLT should be followed until it resolves to baseline or appears to have stabilized for a minimum of 4 weeks. During follow-up subjects should be seen as often as medically indicated to assure safety.

5.5.3. Management of Dose-Limiting Toxicities or Other Urgent Situations

In all cases investigators are free to employ any measures or concomitant medications, following discussion with sponsor, necessary to optimally treat the subject.

5.6. Dose Adjustment of Study Drug

5.6.1. Planned Dose Adjustments

Cohort dose escalation is described in Section 4.1. Intrasubject dose escalation of INCB050465 will be allowed during dose escalation, provided that the following criteria are met:

- The Protocol inclusion criteria are met.
- The subject has received 4 cycles of study drug and has not had a related or possibly related toxicity \geq Grade 2.
- The next dose level has been determined to be safe based on DLT rules (eg, no DLTs during Cycle 1).
- The subject is willing to submit to all visits and procedures as in Cycle 1 per the Protocol, except the PK [REDACTED] sampling will only be done as on Cycle 1 Day 15 (Day 1 and Day 8 PK [REDACTED] sampling will not be done).
- In the opinion of the investigator, the subject does not have any concurrent condition or circumstance that would complicate the dose escalation or PK sampling, or pose increased risk to the subject.
- The intrasubject dose escalation has been approved by the sponsor.

5.6.2. Criteria and Procedures for Dose Interruptions and Dose Reductions of INCB050465 and INCB039110

In some circumstances, it may be necessary to temporarily interrupt treatment as a result of adverse experiences that may have an unclear relationship to study drug. Treatment with INCB050465, the combination with INCB039110, or the combination with standard therapies may be delayed up to 2 weeks to allow for resolution of toxicity. If treatment needs to be interrupted in subjects receiving the combination of INCB050465 and INCB039110 for toxicities with unknown causality, both study medications should be held. However, based on the evolving experience with the study treatments, the suspected causal agent only may be held (while the other study treatment continues) until resolution of toxicity following consultation and approval with the medical monitor. Subjects may resume treatment if no medical condition or other circumstance exists that, in the opinion of the investigator, would make the subject unsuitable for further participation in the study. The treating investigator should contact the sponsor's medical monitor to discuss the case of any subject whose treatment has been delayed for more than 14 days before treatment with INCB050465 or the combination of INCB050465

and INCB039110 may be restarted (see [Table 4](#)). Dose reductions of 1 or both (as applicable for subjects on combination therapy) study treatments may be necessary as described in [Table 4](#). For subjects who start on the 300 mg QD dose of INCB039110, the first dose reduction would be to 200 mg QD. If subjects start at a 200 mg QD dose of INCB039110, the combination of INCB050465 with INCB039110 at a lower dose (eg, 100 mg QD) will be subject to discussion with the sponsor. Alternatively, INCB039110 may be discontinued if dose reduction is indicated, and subjects may continue on INCB050465 monotherapy if they continue to receive benefit.

Because subjects may enter the study with extensive pretreatment and/or severe bone marrow infiltration by the primary disease, these dose-reduction rules are provided as guidelines. Individual decisions regarding dose reduction should be made using clinical judgment and in consultation with the sponsor's medical monitor, taking into account relatedness of the AE to the study drug and the subject's underlying condition. Subjects receiving dose reductions (but not meeting DLT criteria) during the first cycle will not be considered evaluable for the purposes of determining the MTD.

Table 4: Guidelines for Interruption and Restart of Study Drug

TOXICITY/NCI CTCAE GRADE	ACTION TAKEN
Chemistries:	

 Total bilirubin > 3.0 × ULN AST and/or ALT > 3.0 × ULN ALP ≥ 2.5 × ULN 
Note: For ALP increases in subjects with bone metastasis-related ALP elevation at baseline, contact sponsor to discuss clinical management and possible dose reductions.
	
Step 1: Interrupt study drug(s) up to 2 weeks (14 days) until the toxicity has resolved to ≤ Grade 1 except ALT/AST elevations, which may require 4 weeks (28 days) to resolve.
 
Step 2: Restart study drug(s) at next lower dose (or INCB050465 at 25% reduction if in expansion cohorts, rounded down to the nearest pill strength); monitor as clinically indicated.^a
 
Dose reductions may be made solely to the suspected agent if the causality can be reasonably assigned to that agent based on existing data (refer to the INCB050465 IB and INCB039110 IB) with approval of the medical monitor.

Hematologic:	

 ANC < 1.0 × 10⁹/L for subjects who enrolled with ANC > 1.5 × 10⁹/L ANC < 0.5 × 10⁹/L for subjects who enrolled with ANC ≤ 1.5 × 10⁹/L Platelet count is 50 to < 75 × 10⁹/L for subjects who enrolled with platelets > 100 × 10⁹/L Platelet count is < 50 × 10⁹/L for subjects who enrolled with platelets ≤ 100 × 10⁹/L 	
Step 1: Interrupt study drug(s) up to 2 weeks (14 days) until the toxicity has resolved to ≤ Grade 1 or pretherapy baseline.
 
Step 2: Restart study drug(s) and monitor as clinically indicated.
 
Dosing interruption may be made solely to the suspected agent if the causality can be reasonably assigned to that agent based on existing data (refer to the INCB050465 IB and INCB039110 IB) with approval of the medical monitor.

 Grade 4 ANC (< 0.5 × 10⁹/L) lasting 7 days ≥ Grade 3 ANC with an oral temperature of at least 38.5°C OR with ≥ Grade 3 infection Platelet count is < 50 × 10⁹/L for subjects who enrolled with platelets > 100 × 10⁹/L Platelet count is < 25 × 10⁹/L for subjects who enrolled with platelets ≤ 100 × 10⁹/L 	
Step 1: Interrupt study drug(s) up to 2 weeks (14 days) until the toxicity has resolved to ≤ Grade 1.
 
Step 2: Restart study drug(s) at next lower dose (or INCB050465 at 25% reduction if in expansion cohorts) and monitor as clinically indicated.^a
 
Dose reductions may be made solely to the suspected agent if the causality can be reasonably assigned to that agent based on existing data (refer to the INCB050465 IB and INCB039110 IB) with approval of the medical monitor.

Table 4: Guidelines for Interruption and Restart of Study Drug (Continued)

TOXICITY/NCI CTCAE GRADE	ACTION TAKEN
Other drug-related toxicities or toxicities not attributable to other causes:	
Diarrhea/colitis (Grade 1)	Step 1: Treat with antimotility agents (eg, 4 mg loperamide followed by 2 mg every 4 hours or after every unformed stool) and initiate supportive care (see Section 5.6.2.1). If not improved after 48 hours, treat per guidance for \geq Grade 2.
Diarrhea/colitis (\geq Grade 2)	Step 1: Interrupt INCB050465. Perform work-up for infection (including CMV, C. difficile , etc). Initiate or continue supportive care (see Section 5.6.2.1). Consider colonoscopy with biopsy for \geq Grade 3. Step 2: If infection is ruled out, start oral steroids, or consider IV steroids if subject is being given IV fluids. If no improvement with oral steroids, switch to IV steroids. When diarrhea resolves to \leq Grade 1, continue supportive care and taper steroids over 4 weeks. When taper is complete and diarrhea is \leq Grade 1, restart INCB050465 at next lower dose in consultation with the medical monitor. If \geq Grade 2 diarrhea reoccurs, permanently discontinue INCB050465.
Pneumonitis (Grade 1)	Step 1: Interrupt INCB050465 until the toxicity has resolved. Step 2: Restart INCB050465 at next lower dose. Monitor as clinically indicated.
Pneumonitis (Grade \geq 2)	Permanently discontinue INCB050465.
Skin toxicity (eg, rash, pruritus, etc, unless otherwise specified) (Grade 2-3)	Step 1: Interrupt INCB050465 until the toxicity has resolved to \leq Grade 1. Step 2: Restart INCB050465 at same dose. If assessed as related to INCB050465, restart at next lower dose in consultation with the medical monitor.
Exfoliative dermatitis (Grade 1)	Step 1: Interrupt INCB050465 until the toxicity has resolved. Step 2: Restart INCB050465 at next lower dose. Monitor as clinically indicated.
Exfoliative dermatitis (\geq Grade 2)	Permanently discontinue INCB050465.
Intestinal perforation (any grade)	Permanently discontinue INCB050465.
Pneumocystis jiroveci pneumonia infection	Interrupt INCB050465. Permanently discontinue INCB050465 if Pneumocystis jiroveci pneumonia infection is confirmed.
CMV infection	Subjects with CMV viremia without associated clinical signs of CMV infection should be carefully monitored. Consider interrupting INCB050465 for subjects with CMV viremia and clinical signs of infection until the infection has resolved. Restart INCB050465 reduced by 1 dose level if approved by the medical monitor.
Varicella zoster infection	Interrupt INCB050465. Restart INCB050465 only by approval of the medical monitor.
Any Grade 1 or 2 toxicity unless otherwise specified	Continue study drug treatment(s); monitor as clinically indicated.

Table 4: Guidelines for Interruption and Restart of Study Drug (Continued)

TOXICITY/NCI CTCAE GRADE	ACTION TAKEN
Any Grade 2 or 3 toxicity, if clinically significant and not manageable by supportive care unless otherwise specified	
Step 1: Interrupt study drug(s) up to 2 weeks (14 days) until toxicity resolves to \leq Grade 1 or medical monitor approval.
 
Step 2: Restart study drug(s) at next lower dose for events considered to be drug-related (or 25% reduction if in expansion cohort, rounded down to the nearest pill strength); monitor as clinically indicated.^a
 
Dose reductions may be made solely to the suspected agent if the causality can be reasonably assigned to that agent based on existing data (refer to the INCB050465 IB and INCB039110 IB) with approval of the medical monitor.

Any recurrent Grade 2 or 3 toxicity after 2 dose reductions	Discontinue study drug treatment(s) and follow-up per Protocol.
Any other Grade 4 toxicity	Discontinue study drug(s) and follow-up per Protocol. However, if toxicity resolves to \leq Grade 1 within 2 weeks, may restart treatment at 1 dose level lower with medical monitor approval.

CMV = cytomegalovirus; IV = intravenous.

^a Note: Only 2 dose reductions due to AEs are permitted.

